Physical examination, vital signs, weight	X	X ¹	X	X	X	X		X		X	X	
ECOG performance status	X	X ¹	X	X	X	X		X		X	X	
Skeletal survey ²	X											
Bone marrow ³	X	X ¹				X						
ECG	X											
CBC with differential	X	X ¹	X	X	X	X	X	X	X	X	X	
Research blood sample (10mL EDTA, 10mL Heparin)	X	X	X	X	X	X		X				
Calculated creatinine clearance (by Cockcroft-Gault) ⁴	X	X ¹				X ⁴		X ⁴		X ⁴		
TSH ⁵	X ⁵	X ¹						X ⁵		X ⁵	X ⁵	
SPEP w m-spike, 24hr urine w m-spike, serum and urine immunofixation, serum quantitative immunoglobulins, serum free light chain assay, beta-2 microglobulin,	X	X ¹				X		X		X	X	
Complete metabolic panel	X	X ¹	X	X	X	X	X	X	X	X	X	
LDH, phosphorus, uric acid	X	X ¹										
Pregnancy testing ⁷	X ⁸	X ⁸	X ⁸	X ⁸	X ⁸	X ⁸		X ⁸		X ⁸	X ⁸	
Register patient into RevAssist® program ⁹	X ⁹											
Prescribe lenalidomide via RevAssist® ¹⁰		X ¹⁰				X ¹⁰		X ¹⁰		X ¹⁰		
Azacitidine administration		X ¹¹										
Dexamethasone prescription		X ¹²				X ¹²		X ¹²				
Response assessment ¹³						X		X		X	X	
Record adverse events ¹⁴		X	X	X	X			X		X	X ¹⁴	
Record concomitant therapies/procedures	X	X				X		X		X	X	
Obtain Follow-Up anti-cancer treatments												X
Obtain Follow-Up survival information												X

* Variations of ± 3 days of the scheduled visit are permitted.

If Physical examination, vital signs, weight and ECOG performance status were done within 7 days of Day 1, they do not need to be repeated at Study Day 1. An unscheduled visit can occur at any time during the study. Source must be maintained for these unscheduled visits. The date for the visit and any data generated must be recorded on the appropriate CRF. Source documents for these unscheduled visits must also be maintained.

Version: 07/16/2015

¹ If screening assessments were done within 7 days of Day 1, they do not need to be repeated at Study Day 1.

² A skeletal survey may be obtained up to 28 days before day 1, cycle 1. It will be repeated every 12 months or earlier if symptoms suggest bony progression.

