5.5.2 Bone Marrow Examinations

Two 20mL syringes, each pre-filled under sterile conditions with 2mL heparin will be used to obtain 40mL bone marrow aspirate on day 1 (or up to 7 days prior) of the first cycle and on day 1 of the second cycle, each time before drug administration. After isolation of mononuclear cells using the Ficoll™ method, CD34+ cells and CD138+ cells will be purified using 2 purification steps with Miltenyi columns followed by flow cytometric assessment of achieved purity. Samples of at least 70% purity will be used to assess DNA demethylation and mRNA reactivation. DNA and RNA of purified cells will be harvested using the Qiagen AllPrep DNA/RNA mini kit™, which allows for column-based isolation of DNA and RNA from the same sample. Isolated RNA and DNA will be stored at -80°C. Within 30 days (once a month) RNA samples will be transcribed into cDNA using Superscript III (Invitrogen™), then stored at -80°C until further analysis. The Illumina® HT12 array will be used to analyze global gene expression in CD138+ cells. DNA methylation profiling will be performed using the Illumina® HumanMethylation27 BeadChip array in CD138+ and CD34+ cells according to the manufacturer's instructions including bisulfite modification using Zymo™ kits. For approximately 10 selected sample genes, changes in expression after cycle one will be confirmed using real-time RT-PCR (TaqMan, Applied Biosystems™).

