5.5.4 Data Analysis

Promoter demethylation after cycle 1 in bone marrow cells enriched either for CD138 or for CD34 expression will be measured using Illumina™ array technology. The Illumina™ bead array software assigns each CpG region tested a number between 0 and 1.0 representing the degree of DNA methylation from 0 to 100%. The number of genes changing their methylation status significantly according to Illumina™ Bead Studio software, version 3 and the number of genes changing their methylation score by at least 0.2 points absolute will be analyzed and will be made publicly available. [name] will assist in the analysis and if necessary, additional help will be obtained from the Cleveland Clinic department of quantitative health sciences. If differences in purity occur between pre-and post-treatment samples this will be taken into account in the statistical analysis.

Changes in global gene expression (Illumina® HT12 array) after cycle one of therapy at the HTLD / HTLD-CKD in bone marrow cells enriched for CD138 will be analyzed by the Illumina™ Bead Studio software, version 3. Genes statistically significantly up- or downregulated at least 2, 5, and 10 fold will be analyzed for each patient and will be made publicly available. [name] will assist in the analysis and if necessary, additional help will be obtained from the Cleveland Clinic department of quantitative health sciences. If differences in purity occur between pre-and post-treatment samples this will be taken into account in the statistical analysis.

To confirm reactivation of about 10 selected sample genes in CD138+ and CD34+ cells, real-time RT-PCR will be performed in triplicates and reported for each gene analyzed with mean and standard deviation of expression after compared to before cycle one.

DNMT1 suppression will be analyzed after above outlined immunohistochemistry protocol. Image files will be loaded into the Image-Pro Plus environment and individual cells will be segmented for quantification of fluorescence signal with the "count/size" function of Image-Pro Plus. Precise segmentation will be achieved by setting a lower threshold just above background emission. A filter will then be set for an area of whole

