5.6.2 Dosing Regimen

The trial will use a classical 3x3 phase I design for patients with GFR > 60ml/min and a modified 3x3 design for patients with GFR 30-59ml/min with enrollment of ten additional patients at the highest tolerated low dose (HTLD / HTLD-CKD) of azacitidine as outlined under 5.1. The dosing schedule is outlined below. Assigned combination treatment with lenalidomide, azacitidine, and dexamethasone will be continued for six 28-day cycles followed by maintenance treatment with lenalidomide single agent at the last tolerated dose until disease progression with adjustment of dose as outlined under 5.7.1 and 5.7.3.

Peripheral blood stem cell harvesting and high dose chemotherapy therapy may be performed at any point after treatment cycle #2. In such patients protocol therapy will be permanently discontinued at least five days before stem cell mobilization begins but in addition to the basic follow up outlined under 2, schedule of study assessments, their peripheral blood stem cell yield and engraftment will be documented.

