5.7.4 Instructions for Initiation of a New Cycle

A new course of treatment may begin on the scheduled Day 1 of a new cycle if:

- The ANC is $\geq 1000/\text{mm}^3$ (G-CSF is allowed to achieve this threshold)
- The platelet count is $\geq 50,000/\text{mm}^3$ (During the first 4 cycles platelet transfusions are allowed to achieve this threshold)
- Any new drug-related neuropathy or rash other than injection site reaction that may have occurred has resolved to \leq grade 1 severity;
- Any bicarbonate decrease below 20mEq/L that may have occurred has resolved to baseline.
- Calculated creatinine clearance $\geq 30\text{ml}/\text{min}$ (by Cockroft-Gault), after 12 cycles on therapy, determining the creatinine clearance every 2 months will suffice
- Any other drug-related adverse events that may have occurred have resolved to \leq grade 2 severity. Physician discretion may be used in initiating the next cycle of treatment if the only toxicities that have not resolved to \leq grade 2 severity are dexamethasone-related toxicities.

If these conditions are not met on Day 1 of a new cycle, the subject will be evaluated weekly and a new cycle of treatment will not be initiated until the toxicity has resolved as described above. If criteria to initiate a new cycle are not met by 21 days after the planned start of a new cycle patients go off study. If a lenalidomide or azacitidine dose reduction was taken during the previous cycle, and the cycle was completed without requiring further dose modification, then the next cycle will start at the same reduced dose. **If lenalidomide and / or azacitidine dosing was omitted for the remainder of the previous cycle or if the new cycle is delayed due to toxicity newly encountered on the scheduled Day 1**, then the new cycle will be started with a one-level dose reduction of lenalidomide and/or azacitidine as appropriate. Dose reductions should generally be taken one drug at a time based on attribution of toxicity to one of the drugs unless otherwise indicated in Section 5.7.3.

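### Monthly reverse transcription puts nearly every patient's before and after RNA in different runs, so the RT-PCR contrast is confounded with the run

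*Combined protocol and SAP*

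**What the plan says.** Section 5.5.2 (Bone Marrow Examinations) takes the paired aspirates "on day 1 (or up to 7 days prior) of the first cycle and on day 1 of the second cycle". Section 5.6.2 gives the cycle length: combination treatment "will be continued for six 28-day cycles". The footnote to the Section 2 schedule adds "Variations of ± 3 days of the scheduled visit are permitted". Section 5.7.4 lets cycle 2 start late, up to a limit: "If criteria to initiate a new cycle are not met by 21 days after the planned start of a new cycle patients go off study".

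Isolated RNA and DNA are kept at -80°C. For the RNA, Section 5.5.2 then states: "Within 30 days (once a month) RNA samples will be transcribed into cDNA using Superscript III". The cDNA is "then stored at -80°C until further analysis".

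Section 5.5.4 (Data Analysis) uses the material in two ways:

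- About 10 selected genes are confirmed by RT-PCR in triplicate, in CD138+ and CD34+ cells, and reported as expression after compared with before cycle 1.
- For the HT12 array in CD138+ cells, "Genes statistically significantly up- or downregulated at least 2, 5, and 10 fold will be analyzed for each patient".

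The only technical difference that Section 5.5.4 promises to take into account is sample purity. Sections 5.5.2 and 5.5.4 mention no transcription of a patient's two samples together, no control RNA carried across runs and no run term in the analysis.

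**The concern.** The planned comparison is within the patient, and the two samples are about one run interval apart. A pre-treatment sample that must be transcribed within 30 days will usually be processed before its partner reaches a run. Within that patient, after treatment and later transcription run are then the same contrast, and no later analysis of that pair can separate them. Triplicates do not help if they are PCR replicates of one cDNA, because all three carry the same run effect. A reference gene, if one were used, would remove a shift common to all genes in a run but not a gene-specific one.

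Gene reactivation after cycle 1 is a secondary endpoint (Section 4.2.2). The synopsis says it should help show whether the chosen dose has its expected effect in myeloma cells before a larger trial. RT-PCR is the confirming step, so it is the step that most needs a clean before/after comparison.

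**Working it through.** The plan gives no sample size, power or error rate on this point, so there is no figure of its own to reproduce.

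**Gap between the two marrows (d), from the documents**

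- On schedule: 28 days, plus 0 to 7 days for an early pre-treatment marrow, giving 28 to 35 days.
- With the ±3-day window: 28 − 3 = 25 days at the shortest, 35 + 3 = 38 at the longest.
- With cycle 2 delayed by the permitted 21 days: 35 + 21 = 56 days.

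**Interval between runs (T).** Once a month is about 30 days; 28 to 31 were tried.

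**Assumption.** Runs fall on a regular calendar unrelated to sampling dates. Then P(same run) = max(0, 1 − d/T).

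| d (days) | T = 28 | T = 30 | T = 31 |
|---|---|---|---|
| 25 | 10.7% | 16.7% | 19.4% |
| 28 | 0% | 6.7% | 9.7% |
| 29 | 0% | 3.3% | 6.5% |
| 30 | 0% | 0% | 3.2% |
| 31 or more | 0% | 0% | 0% |

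At T = 30 and d = 28, for example, 1 − 28/30 = 6.7%.

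**Averages.** If the pre-treatment marrow is equally likely to be 0 to 7 days early, the same-run chance is 1.3% (T = 30) to 2.4% (T = 31). Adding a uniform ±3-day window gives 2.1% to 3.2%. So about 97-99% of pairs are split on average, 90-100% at exactly 28 days, and at least about 81% in the most favourable permitted case.

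**In patients.** Section 10.2.3 expects 16-22 patients at the HTLD / HTLD-CKD. At a 2% same-run chance that is 16 × 0.02 = 0.3 to 22 × 0.02 = 0.4 unsplit pairs. If every gap were exactly 28 days (T = 30), it is 16 × 0.067 = 1.1 to 22 × 0.067 = 1.5.

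**Would a run term rescue the cohort mean?** Staggered entry was simulated at about 1.8 patients a month (44 patients / 24 months, assumed uniform), with T = 30 and a separate fixed effect for each run. About 2.5% of the information on the before/after effect remained with gaps of 28 to 35 days, and about 7% with gaps of exactly 28. With gaps of 28 to 35 days the effect was estimable in only 53% of simulated 16-patient cohorts and 65% of 22-patient cohorts.

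**Size of a run effect.** The documents give none. As an illustration only, let the log2 difference in a gene with no drug effect have SD √(2(t² + b²)), where t is the technical SD and b the gene-specific between-run SD. The share of such genes beyond 2-fold is then:

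| | b = 0 | b = 0.1 | b = 0.2 | b = 0.3 |
|---|---|---|---|---|
| t = 0.2 | 0.04% | 0.16% | 1.2% | 5.0% |
| t = 0.3 | 1.8% | 2.5% | 5.0% | 9.6% |

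Beyond 5- or 10-fold the share stays at 0.01% or less. All SDs are assumed. The table ignores the requirement in Section 5.5.4 that a counted gene also be statistically significant, and it bears on the array only if the array uses the monthly cDNA.

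**The case against.** **The array.** A reader might infer that all the expression results are confounded, including the per-patient 2-, 5- and 10-fold counts. The documents do not support this. The synopsis and Section 4.2.2 describe the HT12 input as RNA harvested from the cells. Section 5.5.2 stores RNA at -80°C and says neither that all of it is transcribed monthly nor that the array takes that cDNA. This objection stands: the point is firm for RT-PCR and conditional for HT12.

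**Bias.** A reader might also infer that the average treatment effect is biased. Each run mixes pre-treatment samples of some patients with post-treatment samples of others, so run effects without a trend add noise to a cohort mean. Bias needs drift between runs, and nothing in the documents shows drift. This stands too, but it does not help the individual patient's contrast.

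**The calendar.** Section 5.5.2 sets a limit and a frequency, not run dates. A laboratory could time a run so that a pair 28 to 30 days apart is transcribed together within the limit. That is possible for some pairs, but the plan does not ask for it, and pairs 31 days or more apart cannot meet the limit together.

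**Later batching.** Stored cDNA lets both samples go on one PCR plate. That removes a plate effect, not the effect of the transcription run, which is already fixed.

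**The remedy.** Holding the pre-treatment RNA makes its storage longer than its partner's in every patient, so storage time then goes with treatment in one direction. This is a real cost and must be stated. It does not outweigh removing the run difference, since the protocol already stores RNA at -80°C.

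**Conclusion.** The point holds for the RT-PCR confirmation of about 10 genes in CD138+ and CD34+ cells. With runs at monthly intervals, about 81-100% of pairs are split between runs depending on the gap, and about 97-99% on average. Each split pair confounds after versus before cycle 1 with the transcription run. This rests on a regular run calendar unrelated to sampling dates.

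For the HT12 fold changes it holds only if that array uses the monthly cDNA. The DNA methylation arrays involve no reverse transcription and are not affected. The harm cannot be sized from the documents. Dose finding, safety and clinical response are untouched. It is a cheap improvement to a secondary pharmacodynamic endpoint, worth making because the stated rule itself builds in the confounding.

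**What to change.** In Section 5.5.2, replace the monthly rule with:

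> Each patient's pre- and post-cycle-1 RNA is held at -80°C and transcribed together in one run after the cycle 2 day 1 marrow, and the pair is run on the same RT-PCR plate; the transcription run is recorded. For samples already transcribed under the monthly rule, the pair is re-transcribed together if RNA remains; otherwise it is flagged as split-run.

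The second sentence is needed because the synopsis reports that eighteen patients had started treatment before amendment 7. Section 5.5.2 should also say whether the HT12 array takes stored RNA or this cDNA.

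The cost is protocol wording and laboratory scheduling, with no extra samples and no new type of assay; re-transcribing earlier pairs repeats work only where RNA remains. The downside to state is that the pre-treatment RNA is stored about one to two months longer than its post-treatment partner (28 to 35 days on schedule, about 56 with the longest delay), beyond the present 30-day limit. A common control RNA in every run would be an alternative if the laboratory cannot accept that storage. Recording the run without pairing is a weak substitute, as the simulation shows. Placing pairs on the same array chip and converting paired DNA together are optional good practice; neither follows from the transcription rule.

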5.5.3 Blood Studies

EDTA blood samples (10mL purple top) obtained at day one of week 1,2,3,4 and day one of cycle 2,3,4,6 will be used to obtain buffy coats for DNMT1 immunohistochemistry with Q-dot® (Invitrogen™) analysis, according to a protocol that has been validated in samples of AML and MDS patients treated with decitabine in the laboratory of [name]. Briefly, cytopsin slides of buffy coats will be prepared and cells fixed and permeabilized with 10% formalin and 0.25% triton. Non specific binding sites will be blocked with 10% normal goat serum and 6% BSA. Slides will be incubated overnight with mouse anti-DNMT1 antibody (Abcam catalog number ab13537) (diluted 1:500 in blocking solution), followed by a 655 nm Quantum DotsTM-conjugated goat anti-mouse antibody (Invitrogen catalog number Q11022MP) (diluted 1:500). Finally, cells will be stained with 3 µM DAPI for 5 min before dehydration in graded alcohols and toluene before mounting on Qmount™ Qdot™ mounting media (Invitrogen), which provides

Qdot emission stability for up to 8 months. Images will be obtained the next working day.

Heparin tubes (10mL) from the same time points (day one of week 1,2,3,4 and day one of cycle 2,3,4,6) will be used to isolate whole blood DNA using the DNA blood and tissue mini kit® from Qiagen™. This DNA will be stored at -80°C and may later be used to investigate whether genes identified as hypermethylated on the methylation array can be detected in the peripheral blood using pyrosequencing of bisulfite modified DNA. A PyroMark Q24® sequencer in [name] laboratory will be used for these studies.

Plasma from heparin tubes will be collected and frozen at -80°C for later determination of the activity of the azacitidine inactivating enzyme cytidine deaminase (CDA). This will be performed by an HPLC method optimized in [name] laboratory, which quantifies deamination of added cytidine. The enzymatic activity is determined by comparison of cytidine deamination achieved by plasma samples with deamination achieved by incubation of cytidine with dilutions of pure CDA enzyme standards.

5.5.4 Data Analysis

Promoter demethylation after cycle 1 in bone marrow cells enriched either for CD138 or for CD34 expression will be measured using Illumina™ array technology. The Illumina™ bead array software assigns each CpG region tested a number between 0 and 1.0 representing the degree of DNA methylation from 0 to 100%. The number of genes changing their methylation status significantly according to Illumina™ Bead Studio software, version 3 and the number of genes changing their methylation score by at least 0.2 points absolute will be analyzed and will be made publicly available. [name] will assist in the analysis and if necessary, additional help will be obtained from the Cleveland Clinic department of quantitative health sciences. If differences in purity occur between pre-and post-treatment samples this will be taken into account in the statistical analysis.

Changes in global gene expression (Illumina® HT12 array) after cycle one of therapy at the HTLD / HTLD-CKD in bone marrow cells enriched for CD138 will be analyzed by the Illumina™ Bead Studio software, version 3. Genes statistically significantly up- or downregulated at least 2, 5, and 10 fold will be analyzed for each patient and will be made publicly available. [name] will assist in the analysis and if necessary, additional help will be obtained from the Cleveland Clinic department of quantitative health sciences. If differences in purity occur between pre-and post-treatment samples this will be taken into account in the statistical analysis.

To confirm reactivation of about 10 selected sample genes in CD138+ and CD34+ cells, real-time RT-PCR will be performed in triplicates and reported for each gene analyzed with mean and standard deviation of expression after compared to before cycle one.

DNMT1 suppression will be analyzed after above outlined immunohistochemistry protocol. Image files will be loaded into the Image-Pro Plus environment and individual cells will be segmented for quantification of fluorescence signal with the "count/size" function of Image-Pro Plus. Precise segmentation will be achieved by setting a lower threshold just above background emission. A filter will then be set for an area of whole

cells to exclude fluorescent fragments from the measurement. Image-Pro Plus generates a high-content array of measurements that include event number, area, mean of pixel intensities, and maximum and minimum pixel intensities. These scores will be integrated into a mean intensity fluorescence (MIF) score using the Image-Pro Plus software. The mean and standard deviation of reduction in MIF scores after treatment with azacitidine at the studied time points will be reported for all tested dose levels.

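### The array endpoints have no stated alpha, false-discovery control or paired across-patient analysis, and the unit behind the RT-PCR standard deviation is undefined

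*Combined protocol and SAP*

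**What the plan says.** All of the pharmacodynamic analysis plan is in section 5.5.4.

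- **Methylation, first count:** "The number of genes changing their methylation status significantly according to Illumina™ Bead Studio software, version 3". The sentence gives no unit of analysis.
- **Methylation, second count:** "the number of genes changing their methylation score by at least 0.2 points absolute will be analyzed and will be made publicly available". No test is attached to it.
- **Expression:** "Genes statistically significantly up- or downregulated at least 2, 5, and 10 fold will be analyzed for each patient". Here the unit is the patient, and a gene must pass both the significance call and a fold-change tier.
- **RT-PCR for about 10 genes:** "real-time RT-PCR will be performed in triplicates and reported for each gene analyzed with mean and standard deviation of expression". The comparison is between the samples on either side of the first cycle. Whether the spread is over the three replicates or over patients is not said.
- **Purity:** "If differences in purity occur between pre-and post-treatment samples this will be taken into account in the statistical analysis". The method is not given.
- **DNMT1:** "The mean and standard deviation of reduction in MIF scores after treatment with azacitidine at the studied time points will be reported for all tested". This summary, given by dose level, uses neither a software call nor triplicates.

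Section 5.5.2 schedules one marrow before the first cycle and one on day 1 of the second, and admits samples of at least 70% purity. Section 10.1 names the software. Sections 10.2.7 and 10.3 send the reader back to 5.5. None of them adds a test, an alpha or a multiplicity rule for the arrays.

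**The concern.** Sections 1 and 3.3 give the pharmacodynamic effect in myeloma cells as one reason for the 10-patient extension, ahead of a possible larger phase II trial. Section 5.5 notes that reactivation has not yet been shown in the myeloma cells of treated patients. That is a question about the dose, so the evidence has to recur across patients.

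The stated analysis does not reach that question. For expression it yields a gene list per patient. For methylation it yields counts, with no stated way of combining patients. Neither output comes with an error rate or with a reference for what would appear without a drug effect. The samples are naturally paired, yet the pairing is not used across patients. The gene-level results are to be made public, so readers would have to judge them without knowing the threshold behind each call.

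**Working it through.** **1. The plan's own figures.** No alpha, power or sample size is given for these endpoints. The enrolment figures do reproduce. From section 1: 18 started + (6 − 2) to fill dose level 5 + 6 + 6 at two CKD levels + 10 extension = 44, as stated. Section 10.2.3 gives 16-22 patients at the HTLD / HTLD-CKD: 6 + 10 = 16 and 6 + 6 + 10 = 22. So 16-22 is the ceiling for usable pairs. The purity filter and missing second marrows can lower it.

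**2. What a within-patient call can test.** Write the change for gene g in patient i as d = δ(g) + b(i,g) + e(i,g): the mean effect, that patient's departure from it (including sampling), and assay error. With one marrow on each side, a call inside one patient can set d only against assay error. It cannot test δ(g), because b is not estimated. A paired analysis across patients estimates b and e together.

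**3. False calls if unadjusted.** The documents give neither the number of features m nor alpha, so both are assumed. Expected false calls per patient and cell type with no true change = m × alpha:

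| m | alpha 0.05 | 0.01 | 0.001 |
|---|---|---|---|
| 10,000 | 500 | 100 | 10 |
| 25,000 | 1,250 | 250 | 25 |
| 50,000 | 2,500 | 500 | 50 |

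Under independence, the chance of at least one false call exceeds 0.999 in every cell. A Bonferroni limit, 0.05/m, would be 5e-6, 2e-6 and 1e-6.

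**4. The effect-size filters.** With assay SD s per array, noise alone gives a change with SD s√2. The expected number passing a filter c is m × 2[1 − Φ(c/(s√2))]. At m = 25,000, with s assumed:

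- Change of at least 0.2: about 0.1 genes if s = 0.03, 117 if 0.05, 1,084 if 0.07.
- Change of at least 2 fold (log2 scale, c = 1): about 0 if s = 0.1, 10 if 0.2, 461 if 0.3.
- Changes of 5 and 10 fold: near 0 for s up to 0.3.

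The expression lists also require a significance call, so the fold-change figures are upper limits under each assumed s.

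**5. What recurrence adds.** Take alpha 0.05 and m = 25,000, with independent calls. The expected number of genes called by chance in at least k of n patients is m × P(Binomial(n, 0.05) ≥ k): 1,073 for 3 of 16, 2.0 for 6 of 16, and 0.17 for 8 of 22. Combining patients removes most chance calls.

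**6. RT-PCR, log2 scale.** Assume technical SD t = 0.1 to 0.3 and between-patient SD B = 0.5 to 1.5. The single-replicate technical SD of a change is t√2. The SD of patient-level changes, after averaging triplicates, is √(B² + 2t²/3).

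- t = 0.3, B = 0.5: 0.557 / 0.424 = 1.3.
- t = 0.1, B = 1.5: 1.502 / 0.141 = 10.6.

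A triplicate SD would therefore understate the spread by a factor of about 1.3 to 10.6. With 16 or 22 pairs the 95% interval half-width for the mean change is about 0.2 to 0.8, so an across-patient estimate is feasible.

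**7. Purity.** A rise from 70% to 100% moves a methylation score by 0.3 × the difference in methylation between target and contaminating cells. It reaches 0.2 when that difference is 0.2/0.3 = 0.67 or more.

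**The case against.** Several stronger readings are tempting, and the documents do not support them.

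- **That every array call is made per patient.** Only the expression sentence says so. The methylation sentence leaves the unit open.
- **That the RT-PCR SD is technical.** The sentence reports by gene, and a mean and SD over patients is at least as natural a reading. The defect is ambiguity.
- **That about 1,350 loci per patient would be false.** That multiplies a feature count guessed from the array's name (27,000) by a 5% level found nowhere in the plan, and assumes no correction. It also does not describe the expression rule, which adds fold-change tiers.
- **That the results would be mostly assay noise.** Step 4 runs from almost none to over a thousand genes, depending on assay SDs the documents do not give.
- **That purity is ignored, or that all pharmacodynamics are affected.** Purity is measured and an adjustment is promised. DNMT1 lies outside this point.

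Two further arguments carry weight. Section 3.3 expects different silenced genes in different clones and patients, so a locus-by-locus test across patients can miss a real effect that per-patient counts would show. That is a reason to keep the counts, but it does not supply an error rate. Secondly, usable pairs may be few, and pooling the two renal-function groups mixes lenalidomide doses and possibly azacitidine doses.

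The existing safeguards close the gap only partly. The 2-fold tier and the 0.2 count depend on unstated noise. RT-PCR uses RNA from the same cell populations, so it can confirm a measurement but cannot separate a drug effect from a purity or sampling difference. The software may offer false-discovery control, but the plan does not require it.

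**Conclusion.** The point holds as a gap in method. No alpha, no false-discovery control and no paired across-patient analysis is specified for the array endpoints, and the unit of the RT-PCR SD is undefined. Within-patient expression calls cannot show which changes recur at the HTLD / HTLD-CKD. For methylation, no way of combining patients is stated.

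The number of false calls is not known. The range of about 10 to 2,500 per patient and cell type holds only if the software call is unadjusted, for the assumed feature counts and alphas, and before the fold-change filters. The conclusion about recurrence rests on none of those assumptions.

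The consequence is limited. These are secondary endpoints and play no part in choosing the HTLD or HTLD-CKD. They do bear on one of the reasons given for the extension, so the change should be made.

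**What to change.** In section 5.5.4:

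1. Add a paired pre/post test for each locus and gene, across patients at the HTLD / HTLD-CKD with usable pairs, with Benjamini-Hochberg FDR at 5%. Name the test and the software settings.
2. Enter the measured purity change as a covariate. This supplies the method for the adjustment already promised.
3. Show HTLD and HTLD-CKD separately as well as pooled.
4. Keep the per-patient counts as description, because reactivated genes may differ between patients.
5. For RT-PCR, average triplicates within patient, then report the mean and SD of the paired log fold change across patients.

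No new sample or visit is needed. The cost is a little analysis time, shorter gene lists, and limited power with at most 16-22 pairs. Power will be lower still when the two groups are shown separately.
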